5.2.2 Subject Exclusion Criteria

Study subjects meeting any of the following criteria during screening evaluations will be excluded from entry into the study:

1. History of urolithiasis.
2. Urine pH < 5.5 at screening (as acidic urine is a major determinant of uric acid urolithiasis).
3. History of gout.
4. History of stroke or myocardial infarction.
5. History of symptomatic coronary artery disease (e.g. angina pectoris) or symptomatic peripheral arterial disease within 1 year prior to Screening.
6. Symptomatic congestive heart failure with a documented ejection fraction below 45%.
7. Poorly controlled arterial hypertension (SBP>160mmHg or DBP>100mmHg at Screening).
8. Women who are pregnant or lactating.
9. The presence of unstable psychiatric disease, cognitive impairment, or dementia that would impair ability of the subject to provide informed consent, according to Site Investigator judgment, or a history of active substance abuse within the prior year.
10. Anything that, in the opinion of the Site Investigator, would place the subject at increased risk or preclude the subject's full compliance with or completion of the study.
11. Use of the following within 30 days prior to Screening: inosine, allopurinol, probenecid, more than 300mg vitamin C daily (note that a subject may take a standard multivitamin up to one tablet or capsule daily). Use of thiazides is permissible as long as the subject is on a stable dose from 1 week prior to Screening.
12. Known hypersensitivity or intolerability to inosine.
13. Renal insufficiency as defined by eGFR < 60 mL/min/1.73m² at Screening.

Participation in other investigational trials for the treatment of patients with ALS is allowed.

5.3 Withdrawal

Study drug will be discontinued if:

- Any clinical adverse event (AE), laboratory abnormality, concurrent illness, or other medical condition or situation occurs such that continued participation in the study would not be in the best interest of the subject.

Subjects are free to withdraw from participation in the study at any time upon request.

Subjects who withdraw from the study will not be replaced.

5.3.1 Handling of Withdrawals

A subject may choose to discontinue participation in the study at any time. However, the Site Investigator or designee will encourage subjects to continue with follow-up, regardless of their compliance with study drug. If a subject who initiated study drug permanently discontinues study drug, the SI or designee should still encourage subjects to follow the study protocol under the

modified intent-to-treat principle (ITT). These subjects will be encouraged to follow the study visits, off drug, up to the final visit. Loss to follow-up should be prevented whenever possible.

Any subject who is on study drug and needs to begin the use of any prohibited medication, must immediately discontinue use of study drug. Subjects who permanently discontinue study drug should return any unused study drug and complete early study drug discontinuation procedures per protocol.

If a subject wishes to withdraw consent, i.e., withdraw his or her participation in future study procedures, the subject will be asked to delay consent withdrawal to allow for a final safety visit and final safety telephone call. The subject will be asked to return to the study site for a final safety visit within 14 days of asking to withdraw consent. The subject will also be asked to have a final telephone call 28 days (+ 5 days) after taking their last dose of study drug.

In the event a subject no longer wishes to have their personal health information used for the analysis of this study, he or she will notify the site through an authorized letter and his or her data will no longer be included as part of the results for this study.

5.3.2 Termination of Study

This study may be prematurely terminated if, in the opinion of the Principal Investigator or Medical Monitor, there is sufficient reasonable cause.

Circumstances that may warrant termination include, but are not limited to:

- Determination of unexpected, significant, or unacceptable risk to subjects.
- Enrollment is unsatisfactory.
- Insufficient adherence to protocol requirements.
- Data that is not sufficiently complete and/or evaluable.

6 TREATMENTS ADMINISTERED

6.1 Treatments

[figure not shown]
6.1.1 Study Product Description

Inosine (chemical name: hypoxanthine 9-β-D-ribofuranoside) is an intermediary metabolite of purine metabolism (structure shown below) that is ultimately converted into urate.

Chemical Formula: C₁₀H₁₂N₄O₅

Molecular Weight: 268.23

adenosine → **inosine** → hypoxanthine → xanthine → urate.

Inosine is a white powder. It is provided by a commercial vendor as 500 mg capsules for oral use.

6.1.2 Treatments administered

Inosine will be administered as one capsule twice a day for the first 3 weeks of the study. Inosine dose will be titrated at Weeks 3, 6, 9, 12 and 16 to target urate levels (7 – 8 mg/dL). Inosine will be provided to each subject in individually labeled containers by the site research pharmacy.

The following pre-specified titration algorithm will be used to adjust inosine dose based on urate levels measured at Weeks 3, 6, 9, 12 and 16.

- 1- Serum urate < 67% increase from most recent level to lower limit of target range (7 mg/dL) ==> increase by 2 caps/day, except:
 - If subject is already on 5 caps/day, then increase by 1 cap/day up to 6 caps/day.
 - If subject is already on 6 caps/day, then continue at this dose.
- 2- Serum urate 67-less than 100% increase from most recent level to lower limit of target range (7 mg/dL) ==> increase by 1 cap/day, except:
 - If subject is already at 6 caps/day, then continue at this dose.
- 3- Serum urate within target range (7-8 mg/dL) ==> no change.
- 4- Serum urate > upper limit of target range (8.1 mg/dL or higher) but \leq 9.0 mg/dL ==> reduce by 1 cap/day the dose being taken at the most recent visit, except:
 - If subject was already down to 1 cap/day, s/he will continue at 1 cap/day.
- 5- Serum urate > 9.0 mg/dL ==> hold treatment (i.e., take 0 caps/day) x 7 days, and then resume treatment at 1 less cap/day than the prior dose (i.e., at the most recent visit), except:
 - If that reduction results in no caps being taken, then continue the hold (i.e., 0 caps/day) x 7 more days, then resume treatment at 1 cap/day.
- 6- If a subject returns 3 consecutive serum urate levels > 9.0 mg/dL, then the study drug will be permanently discontinued due to “excess sensitivity to study drug” (This will not be treated as an adverse event (AE)).
- 7- If a subject’s baseline level is \geq 7.0 mg/dL, study drug will be held until the Week 3 labs.

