4 STUDY DESIGN

4.1 Overall Study Design and Plan

During the enrollment period, approximately 60 subjects will be screened at up to three (3) Northeast ALS Consortium (NEALS) Centers in the United States. Approximately 30 of these subjects are expected to be found eligible for study enrollment and will be randomized 2:1 to receive inosine or placebo. Per study protocol, the aim is to elevated serum urate levels only in those subjects whose baseline urate level falls below the predicted median for this population. Approximately 30 subjects will receive inosine or placebo for 20 weeks (administered in the form of 500 mg capsules, 1 to 6 capsules a day for a total daily dose of up to 3 gm). The dose of inosine will be titrated to target urate levels of 7-8 mg/dL based on urate level measurement that will occur at the Week 3, Week 6, Week 9, Week 12 and Week 16 visits. Clinic visits will occur at Screening, Baseline, Week 12, Week 20 and Unscheduled Safety Visits. Telephone visits and remote serum urate testing will occur at Week 3, Week 6, Week 9 and Week 16. There will be a window of ± 3 days for each visit. The Screening Visit must be completed within 21 days of the Baseline Visit. All visit windows are consecutive calendar days and are calculated from the day the participant starts study treatment (Day 0, the day of the Baseline Visit).

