4.3 Study Duration

Subjects will remain on treatment until the Week 20 visit. Each subject will also have a Week 24 Follow-up Telephone Interview to assess for adverse events (AEs), changes in concomitant medications and to administer the ALSFRS-R.

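### The titration rules in Section 6.1.2 break down when urate falls back below 7 mg/dL: read one way they add 2 capsules/day for any shortfall, read another they give no instruction

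*Combined protocol and SAP*

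**What the plan says.** All dose changes follow the algorithm in Section 6.1.2, applied at Weeks 3, 6, 9, 12 and 16. For the starting dose, "Inosine will be administered as one capsule twice a day for the first 3 weeks of the study".

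- **Going up.** Only rules 1 and 2 raise the dose. Both use the percentage "increase from most recent level to lower limit of target range (7 mg/dL"). Below 67%, rule 1 adds 2 capsules/day, limited to 1 capsule at 5/day and none at 6/day. From 67% to below 100%, rule 2 adds 1 capsule/day, with no change at 6/day.
- **In range (7 to 8 mg/dL).** Rule 3 makes no change.
- **Going down.** For 8.1 to 9.0 mg/dL, rule 4 says to "reduce by 1 cap/day the dose being taken at the most recent visit", with a floor: "If subject was already down to 1 cap/day, s/he will continue at 1 cap/day". Above 9.0, rule 5 holds drug for 7 days, "then resume treatment at 1 less cap/day than the prior dose".
- **High baseline.** If baseline urate is 7.0 or above, rule 7 says "study drug will be held until the Week 3 labs".

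Section 4.1 caps exposure at 6 capsules, "for a total daily dose of up to 3 gm". Section 4.3 adds: "Subjects will remain on treatment until the Week 20 visit".

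No rule mentions a subject who was at or above 7.0 at the previous test and is now below 7. Section 7.3 only tells staff to keep or modify the dose to reach target. Section 10.1 refers back to the algorithm for levels that are too high.

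**The concern.** Measuring progress from the previous level makes sense while urate climbs from below 7. It stops making sense once the subject has reached 7, because no increase to 7 remains to be made. A later dip below 7 is ordinary: test-to-test variation can cause it in a subject who was in range, and a rule 4 or rule 5 reduction can cause it after an overshoot.

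Read in plain words, the rules then give the larger step to subjects who may need the smaller one, and can move someone past the dose that has just overshot. Read as a ratio, a supposedly pre-specified algorithm says nothing about a subject below target, and sites could dose identical subjects differently.

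The primary objective is safety and tolerability (Section 3.1). The protocol says that gout generally develops above 8 mg/dL (Section 2.3.1) and lists gouty arthritis and stones as events of special interest (Section 9.1.1). The share of samples in range is also an operational endpoint (Section 10.2.2), so the rule affects a reported result.

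**Working it through.** The plan states no figure for this situation, so there is none to reproduce. The inputs are the rules in Section 6.1.2.

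**1. Which rule applies after a fall.** Let p be the previous level and c the current level, with p at least 7.0 and c below 7.

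- *Plain reading.* Urate has fallen, so the increase is less than 67%. Rule 1 applies whatever the size of 7 - c.
- *Signed-ratio reading.* The share is (c - p)/(7 - p).
  - 7.1 to 6.9: (-0.2)/(-0.1) = 200%.
  - 7.5 to 6.9: (-0.6)/(-0.5) = 120%.
  - 8.5 to 6.9: (-1.6)/(-1.5) = 106.7%.
  - p = 7.0: the denominator is zero.

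  Both terms are negative and the numerator is the larger, so every defined value exceeds 100%. Rules 1 and 2 are not met, and neither is rule 3. No rule applies.
- *Third reading: the most recent level is the one just measured.* At 6.9 the needed rise is (7 - 6.9)/6.9 = 1.4%, so rule 1 gives +2 again. This reading is unlikely to be intended: at 4.0 the needed rise is 3.0/4.0 = 75%, which would give the smaller step to the lower level.

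**2. The plain reading compared at one current level, 6.9 mg/dL.**

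| Previous level | Share of the way to 7 | Step |
|---|---|---|
| 4.0 | 2.9/3.0 = 96.7% | +1 |
| 5.0 | 1.9/2.0 = 95% | +1 |
| 6.0 | 0.9/1.0 = 90% | +1 |
| 7.1 | fall | +2 |
| 8.0 | fall | +2 |

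Two capsules are 1000 mg/day, one third of the 3 g maximum, here for a shortfall of 0.1 mg/dL.

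**3. Dose path after an overshoot on N capsules, then a level below 7 (plain reading).** Rule 4, or rule 5 after its hold, gives N-1 with a floor of 1. Rule 1 then adds 2, subject to its limits.

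| N | After the cut | After rule 1 | Relative to N |
|---|---|---|---|
| 1 | 1 | 3 | +2 |
| 2 | 1 | 3 | +1 |
| 3 | 2 | 4 | +1 |
| 4 | 3 | 5 | +1 |
| 5 | 4 | 6 | +1 |
| 6 | 5 | 6 | 0 |

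A sequence that reaches this: 2 capsules, a low level at Week 3, so 4 capsules; 8.5 at Week 6, so 3 capsules; 6.9 at Week 9, so 5 capsules.

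**4. When it can arise, and for how long.** It can arise at four of the five titration tests (Weeks 6, 9, 12 and 16). The next urate test is 3 to 4 weeks later. A Week 16 step has no later titration point. Calls come 1 to 7 days after the draw (Section 7.3), so nominally on days 113 to 119: 140 - 119 = 21 and 140 - 113 = 27 days to Week 20. With a draw on day 112 ± 3 and Week 20 on day 140 ± 7 (Section 7.5), the range is 133 - 122 = 11 to 147 - 110 = 37 days.

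**5. Frequency: illustration only.** The documents give neither the dose response nor the test-to-test variation. The assumptions are:

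- linear response of 0.5, 0.75, 1.0 or 1.25 mg/dL per capsule;
- test-to-test SD of 0.3, 0.5 or 0.7 mg/dL;
- true baseline 3.5 to 5.4 mg/dL and full adherence;
- plain reading, rule 5 hold days not modelled, 8,000 simulated subjects in each of the 12 settings.

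Under these, 0.6% to 57% of subjects are raised at least once above a dose that had given more than 8.0 (21.6% at 0.75 and SD 0.5). Samples above 8.0 at Weeks 12 to 20 make up 5.5% to 44.8%. The 0.5 response is 3.0/6, the rise in the higher-target group of the Parkinson's trial (Section 2.3.1) if all had taken 6 capsules. The mean dose is not given, so 0.5 is a lower bound.

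**The case against.** The strongest objection is that +2 is only one reading. A reader might infer that the protocol plainly orders 2 extra capsules after any dip. The text does not settle that: as a signed ratio, rule 1 is not triggered at all. This stands, and the point is framed accordingly. It does not rescue the rule, because silence for a subject below target is also a defect.

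A reader might also take the upper simulated figures as a forecast. The documents do not support that. At the only response tied to them, 0.5 mg/dL per capsule, the range is 0.6% to 7.8%, which is under 2 of about 20 inosine subjects (30 at 2:1, Section 4.1; 0.078 × 20 = 1.6). With stable readings, falling from 8.1 or more to 6.9 or less on a one-capsule cut needs at least 1.2 mg/dL per capsule; after a level above 9.0 it needs more than 2.1. Otherwise noise or changed adherence must be involved. This stands for the overshoot path. A dip from 7.1 to 6.9 on an unchanged dose needs only ordinary variation.

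Safeguards limit the harm: the 3 g maximum, rules 4 to 6, urine alkalinization (Section 9.4), safety monitoring (Section 10.1), and Section 6.3, which lets the investigator reduce the dose for adverse events or other reasons. These stand too. They bound the consequence but do not tell staff what to do at the dip.

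Subjects held under rule 7 are not part of the problem: 0 + 2 capsules is the standard starting dose.

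**Conclusion.** The point holds in limited form. Rules 1 and 2 do not work when the previous urate was 7.0 or above and the current one is below 7. On the plain reading the step is +2 (+1 at 5 capsules, 0 at 6) for any shortfall, and the dose ends above the one that overshot for N = 1 to 5. On the ratio reading there is no instruction. Neither result depends on the simulation.

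The frequency is unknown and rests wholly on assumed response and noise. Whether N+1 overshoots again depends on urate rising with dose and on the earlier high reading being representative. A reader might infer that the trial is unsafe or that the target cannot be reached; the documents do not support either. This is a dosing rule that should be corrected, with bounded harm.

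**What to change.** Add one rule to Section 6.1.2, for a subject on drug whose previous level was 7.0 mg/dL or above and whose current level is below 7:

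- Increase by at most 1 capsule/day.
- At this and all later tests, do not raise the dose above the lowest dose that gave a level above 8.0, unless the clinical team decides otherwise. If the subject is already at or above that dose, make no change.
- The clinical team confirms any return to a dose that gave a level above 9.0.

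After an overshoot the path becomes N, N-1, N for N = 2 to 6, and 1, 1, 1 at the floor. The ceiling has to cover later tests. Without it, a subject with 8.2 on 4 capsules, then 6.8 on 3, then 6.9 back on 4 has (6.9 - 6.8)/(7 - 6.8) = 50%, and rule 1 takes the dose to 6. The clinical override matters because one falsely high reading could otherwise hold a subject at too low a dose.

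The cost is a few lines of protocol text, with no added visits or tests and no effect on power. Affected subjects get 500 mg/day less at that test (1000 mg/day less at the floor), and the gap can carry forward. With a weak dose response and noisy tests, the in-range share may stay flat or fall by about 1 percentage point.

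Measuring the percentage from baseline is optional. It would also address the +2 at 6.9 after 6.7 (0.2/0.3 = 66.7%). Spelling out the restart after a rule 7 hold is optional as well.

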6.2 Receiving, Storage, Dispensing

6.2.1 Receipt of Drug Supply

Inosine will be shipped from the central pharmacy to the study research pharmacies.

6.2.2 Storage

The drug supply will be kept at the site research pharmacies in a locked, safe area at controlled room temperature with access limited to those directly involved in the study.

6.2.3 Dispensing of Study Drug

Inosine will be provided to each subject in individually labeled containers by the site research pharmacies. Subject compliance will be determined at the end of the study as detailed below.

6.3 Modification of Study Intervention/Investigational Product for a Subject

Any dosage adjustment, including the reason for and dates of adjustment, will be documented in the CRF for each subject requiring this manipulation. The Site Investigator (SI) or licensed physician Sub-Investigator may reduce the dosage of study drug or discontinue the study drug in its entirety for adverse events (AEs) thought to be related to the study drug or for other reason during the trial (the reason for, and dates of suspension or dose reduction must be documented). If the AE is mild or moderate, the dosage may be reduced until the event improves. The SI may then choose to resume the higher dosage or maintain the subject at a reduced dosage.

If the event is serious or life threatening, and deemed to be definitely drug related, the study drug will be discontinued immediately. Study subjects must remain off the study drug permanently. Subjects may not resume study drug. All AEs will be followed to resolution.

6.3.1 Precautionary suspensions

Investigators may approve a brief non-AE-triggered suspension of study drug employed as a medical precaution (e.g., as in a peri-operative suspension of study drug required by the subject's surgeon for an elective procedure, during a day of potential dehydration as in religious fasting, etc).

6.3.2. Dosage Discontinuation

Reasons for discontinuation of study medication may include an AE, Medical Monitor or Principal Investigator recommendation, protocol deviation, loss-to-follow-up, subject request, or death.

Study subjects who discontinue study drug prematurely (early termination from study) will be encouraged to return for a Final Safety Visit and participate in a Follow-Up Telephone Call 28 days (+ 5 days) after the last dose of study drug.

6.4 Accountability Procedures

At the completion of the study, there will be a final reconciliation of drug consumed and drug remaining. This reconciliation will be logged on the drug reconciliation form, signed and dated. Any discrepancies noted will be investigated, resolved, and documented prior to return or destruction of unused study drug. Drug destroyed on site will be documented in the study files.

6.5 Prior and Concomitant Therapy

Throughout the study, the subject may be prescribed concomitant medications or treatments deemed necessary to provide adequate supportive care provided that the medications are licensed in the United States. All concomitant medications and/or treatments received by a subject should be recorded on the appropriate source document and eCRF.

6.5.1 Prohibited Medications and Contraindications

Prohibited Medications

Throughout the course of the trial, study subjects should not be treated with the following medications. If, for safety or health reasons, or by subject choice, the prohibited medication cannot be stopped, then the study medication should be stopped.

Prohibited medications include:

- Inosine from a different source
- Allopurinol
- Probenecid
- More than 300mg Vitamin C daily (please note that a daily multivitamin containing vitamin C is allowed)

Pregnancy & Nursing Mothers

There are no adequate and well-controlled studies in pregnant women. Subjects or partners of male subjects should not become pregnant during the study or 3 months after stopping study drug. If a female subject becomes pregnant, study treatment must be discontinued immediately.

It is not known whether inosine is excreted in human milk. Caution should be exercised; therefore, no subject should nurse their infant while participating in this study.

7 STUDY SCHEDULE

No study procedures should be performed prior to the signing of the informed consent form (ICF). All subjects will sign an ICF prior to undergoing any study tests or procedures. The VC should be performed first at the visits so as not to fatigue the subject with other testing.

Visit windows are consecutive calendar days and the target visit dates are calculated from the Baseline Visit.

Subjects who withdraw consent or early terminate from the study will be asked to come in for a Final Safety Visit and will have a Final Telephone Interview 28 days (+5 days) after stopping study drug.

7.1 Screening Visit

The following procedures will be performed at an office visit to determine the subject's eligibility for the study:

- Obtain written informed consent from subject
- Assess inclusion and exclusion criteria
- Obtain medical history and demographics
- Obtain ALS diagnosis history
- Perform Pulmonary Function Tests (SVC)
- Perform physical examination
- Perform neurological examination
- Measure vital signs including height and weight
- Collect blood for screening labs
- Review and document concomitant medications and therapies
- Assess and document adverse events (AEs) that occur after subject signs informed consent form (ICF)

7.1.1 Screen Failures

Any subject who signs consent will be considered enrolled in the study. If a subject fails screening, *at a minimum*, the following information should be captured and entered in the Electronic Data Capture (EDC) System if it performed/completed:

- Demographics
- Inclusion and Exclusion criteria
- Reason for screen failure
- Screening labs results

7.2 Baseline Visit

This visit will take place within 21 days of the Screening Visit. The following procedures will be performed:

- Review inclusion and exclusion criteria
- Review and document concomitant medications and therapies
- Assess and document AEs
- Collect blood samples for clinical laboratory assessments (urate level, safety labs)
- Collect urine for urinalysis
- Administer ALSFRS-R questionnaire
- Perform Pulmonary Function Tests (SVC)
- Columbia Suicide Severity Rating Scale (C-SSRS) – Baseline
- Administer first dose of study drug. The subject should be observed at the site for 15 minutes by an appropriate healthcare staff member according to the site's institutional/state regulations to assess medical status and any immediate reaction to the study drug.
- Dispense study medication and dosing diary
- Subjects will be given a written schedule of the Week 3, Week 6, Week 9 and Week 16 phone calls. They will also be provided with laboratory requisition forms for blood draws at a Quest Diagnostics laboratory. They will be instructed to have the blood draw performed on specific days prior to each phone call as detailed below. Subjects will also be provided with written address and contact information of the Quest Diagnostics laboratory that is closest to their place of residence.
- Mobile app installation.

